8.2 Safety assessments

Planned time points for all safety assessments are provided in Table 1.

8.2.1 Clinical safety laboratory assessments

See Table 8 for the list of clinical safety laboratory tests to be performed and Table 1 for the timing and frequency. All protocol-required laboratory assessments, as defined in Table 8, must be conducted in accordance with the laboratory manual and Table 1.

The investigator should assess the available results with regard to clinically relevant abnormalities. The laboratory results should be signed and dated and retained at the centre as source data for laboratory variables.

For information on how AEs based on laboratory tests should be recorded in the eCRF and reported, see Section [8.3.7](#).

Local clinical routine procedures to reduce pain and discomfort from blood sampling in children will be followed, eg, offering topical anaesthesia, coordinated sampling to avoid repeated punctures and use of in-dwelling catheters as appropriate in accordance with ethical and instruction guidelines for paediatric blood sampling. Additional safety samples may be collected if clinically indicated at the discretion of the investigator.

The clinical chemistry, haematology, virology, and urinalysis will be performed at a central laboratory.

Table 8 Laboratory safety variables

| Haematology (complete blood counts with differential) | Clinical chemistry (serum or plasma) |
|--|---|
| B-Haemoglobin (Hb) | S/P-Creatinine |
| B-basophil count differential count (absolute count) | S/P-Bilirubin, total |
| B-lymphocyte differential count (absolute count) | S/P-Alkaline phosphatase (ALP) |
| B-Platelet count | S/P-Aspartate transaminase (AST) |
| B-eosinophil count differential count (absolute count) | S/P-Alanine transaminase (ALT) |
| B-monocytes differential count (absolute count) | S/P-Glucose |
| B-neutrophils differential count (absolute count) | S/P-C-reactive protein |
| White blood cell (WBC) count | S/P-Urea |
| | S/P-Albumin |
| Urinalysis (dipstick) | S/P-Potassium |
| U-Hb/Erythrocytes/Blood | S/P-Calcium, total |
| U-Protein/Albumin | S/P-Sodium |
| U-Glucose | S/P-Creatine kinase (CK) |
| | S-hCG test (Section 8.2.5.3) |
| Virology screen | |
| Hepatitis B surface antigen (HBsAG) ^a | |
| Hepatitis C virus (HCV) | |
| Human immunodeficiency virus (HIV) | |

^a If a positive antibody test from Hepatitis B surface antigen (HBsAG) is received, standard reflex confirmation testing is to be carried out.

8.2.2 Physical examinations

A complete physical examination will be performed and include an assessment of the following: general appearance, respiratory, cardiovascular, abdomen, skin, head and neck (including ears, eyes, nose, and throat), lymph nodes, thyroid, musculo-skeletal (including spine and extremities), and neurological systems.

A brief physical examination will include the following: general appearance, respiratory, cardiovascular, and abdomen systems.

Complete and brief physical examinations will be performed at timelines as specified in [Table 1](#). Investigators should pay special attention to clinical signs related to previous serious illnesses, new or worsening abnormalities may qualify as AEs, see Section [8.3.7](#) for details.

8.2.3 Vital signs

- Body temperature, pulse rate, and blood pressure (BP) will be assessed.
- Blood pressure and pulse measurements will be assessed sitting with a completely automated device with a calibrated manometer using an appropriate paediatric cuff. Manual techniques will be used only if an automated device is not available.
- Blood pressure and pulse measurements should be preceded by at least 5 minutes of rest for the patient in a quiet setting without distractions (eg, television, cell phones).
- Vital signs (to be taken before blood collection for laboratory tests) will consist of 1 pulse and 3 BP measurements (3 consecutive BP readings will be recorded at intervals of at least 1 minute). The average of the 3 BP readings will be recorded in the eCRF.

8.2.4 Electrocardiograms

A 12-lead ECG will be obtained as outlined in [Table 1](#) using the site's own ECG machines after the patient has rested in the supine position for at least 10 minutes.

The investigator or authorised delegate will judge the overall ECG as normal or abnormal and report this evaluation. If abnormal, it will be further documented as to whether the abnormality is clinically significant by the Principal Investigator. For all abnormalities (regardless of clinical significance), the specific type and nature of the abnormality will be documented. Clinically significant findings should also be documented on the AE page of the eCRF if applicable.

The investigator or authorised delegate may add extra 12-lead resting ECG safety assessments if there are any abnormal findings or if the investigator considers it is required for any other safety reason. These assessments should be entered as an unscheduled assessment.

All ECG readings will be digitally stored as source documents. Additionally, ECG readings can be printed and placed in the subject's source file.

8.2.5 Other safety assessments

8.2.5.1 Weight and height

Weight and height will be measured at timelines as specified in [Table 1](#).

Weight and height measurements will be performed in light clothing and with shoes off, using calibrated weighing scales and stadiometer.

The patient's weight will be recorded in kilograms; height will be recorded in centimeters.

8.2.5.2 Medical/surgical history

Details of each patient's medical and/or surgical history will be recorded in the eCRF at timelines as specified in [Table 1](#).

8.2.5.3 Pregnancy test

A serum pregnancy test will be done for FOCBP at screening (Visit 1), and a urine pregnancy test must be performed for FOCBP at each treatment visit prior to IP administration. A positive urine test result must be confirmed with a serum pregnancy test. If the serum test at screening is positive, the patient should be excluded. If a urine pregnancy test at a treatment visit and the confirmatory serum pregnancy test are positive, IP treatment must be discontinued.

Females of childbearing potential will be determined at the discretion of the investigator.

8.2.5.4 Concomitant medications

A list of a patient's concomitant medications will be recorded in the eCRF at timelines as specified in [Table 1](#).

8.2.5.5 Asthma exacerbation

In this study, an asthma exacerbation is defined by a worsening of asthma requiring the use of systemic corticosteroids (or an increase in oral steroid dose for those already on systemic corticosteroids) and/or an emergency department (ED) visit requiring use of systemic corticosteroids and/or an in-patient hospitalization due to asthma. An asthma exacerbation that occurs \leq 7 days following the last dose of systemic steroid, prescribed for a prior exacerbation, will be recorded in the eCRF as the same exacerbation event. Asthma exacerbation information will be collected with a recall period of 'since the last scheduled visit'.

Information on in-patient hospitalizations, number of days in the hospital, and ED visits will be collected by the investigator/authorised delegate at each visit (as shown in [Table 1](#)) and recorded in the eCRF. Asthma-related hospitalization and ED visit information will be collected with a recall period of 'since the last scheduled visit'.

A copy of the medical record should be obtained for exacerbations evaluated and treated at non-study centres (eg, by the primary care health care provider or at an ED/hospital) and details entered into the exacerbation eCRF in a timely fashion. Changes in concomitant medication due to exacerbation must be recorded in the eCRF.

8.3 Collection of adverse events

The investigator is responsible for ensuring that all staff involved in the study are familiar with the content of this section.

The definitions of an AE or SAE can be found in [Appendix C](#).

Adverse events will be reported by the patient (or, when appropriate, by a caregiver, surrogate, or the patient's legally authorised representative).

The investigator and any designees are responsible for detecting, documenting, and recording events that meet the definition of an AE or SAE in the eCRF. For information on how to follow up AEs see Section [8.3.3](#).

8.3.1 Method of detecting AEs and SAEs

Care will be taken not to introduce bias when detecting AEs and/or SAEs. Open-ended and non-leading verbal questioning of the patient is the preferred method to inquire about AE occurrences.

8.3.2 Time period and frequency for collecting AE and SAE information

Adverse events and SAEs will be collected from the time of signature of the ICF throughout the treatment period and including the follow-up period (Visit 14).

All SAEs will be recorded in the eCRF and reported to the sponsor or designee within 24 hours, as indicated in [Appendix C](#). The investigator will submit any updated SAE data to the sponsor within 24 hours of it being available.

Investigators are not obligated to actively seek AE or SAE in former study patients. However, if the investigator learns of any SAE, including a death, at any time after a patient's last visit and he/she considers the event to be reasonably related to the study treatment or study participation, the investigator may notify the sponsor.

The method of recording, evaluating, and assessing causality of AE and SAE and the procedures for completing and transmitting SAE reports are provided in [Appendix C](#).

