1 PROTOCOL SUMMARY

1.1 Schedule of Activities (SoA)

Table 1 Schedule of assessments

| | Part A – PK, PD, Safety | | | | | | | | | | Part B- Safety | | | | DXD/ WD | For details see Section |
|---------------------------------|------------------------------------|----------|----------------|----------------|----------------|----------------|----------------|----------------|----------------|------------|------------------|------------------|------------------------|------------------------|------------|----------------------------------|
| | 1 SCRN Days -28 to -14 | 2 | 3 +1 day | 4 ±3 day | 5 ±4 day | 6 ±7 day | 7 ±7 day | 8 ±7 day | 9 ±7 day | 10 | 11 ±7 days | 12 ±7 days | 13 EOT ±7 day | 14 F/U ±7 day | | |
| Visit | | | | | | | | | | | | | | | | |
| Visit windows | | | | | | | | | | | | | | | | |
| Week | - | 0 | 0 | 1 | 2 | 4 | 8 | 12 | 16 | 24 | 32 | 40 | 48 | 52 | - | Section |
| Day | - | 0 | 1 | 7 | 14 | 28 | 56 | 84 | 112 | 168 | 224 | 280 | 336 | 362 | - | - |
| Written informed consent/assent | X | | | | | | | | | | | | | | | Appendix A 3 |
| Inclusion/exclusion criteria | X | X | | | | | | | | | | | | | | 5.1, 5.2 |
| ACQ-IA | X | X | | X | X | X | X | X | X | X | X | X | X | X | | 8.1.2 |
| PGIC-IA | | | | | | | | | X | X | X | | X | | | 8.1.2 |
| CGIC | | | | | | | | | X | X | X | | X | | | 8.1.2 |
| Body weight and height | X | | | | | | | | X | X | | | X | | | 8.2.5.1 |
| Patient stratification | X | | | | | | | | | | | | | | | 6.1 |
| Vital signs | X | X | X | X | X | X | X | X | X | X | X | X | X | X | | 8.2.3 |
| Medical/surgical history | X | X | | | | | | | | | | | | | | 8.2.5.2 |
| 12-lead ECG | X | | | | | | | | X | | | | X | | | 8.2.4 |

Table 1 Schedule of assessments

| | Part A – PK, PD, Safety | | | | | | | | | | Part B- Safety | | | | | DXD/ WD | For details see Section |
|--|------------------------------------|----------------|-----------|-----------|-----------|----------------|----------------|-----------|----------------|----------------|----------------|----------------|-------------------------|------------------------|---|-----------------|----------------------------------|
| | 1 SCRN Days -28 to -14 | 2 | 3 | 4 | 5 | 6 | 7 | 8 | 9 | 10 | 11 | 12 | 13 EOT ±7 days | 14 F/U ±7 day | | | |
| Visit | | | | | | | | | | | | | | | | | |
| Visit windows | | | +1 day | ±3 day | ±4 day | ±7 day | ±7 day | ±7 day | ±7 day | ±7 day | ±7 days | ±7 days | ±7 day | ±7 day | | | |

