4 STUDY DESIGN

4.1 Overall design

This is an open-label, parallel group study designed to evaluate the PK and PD, and long-term safety of benralizumab administered SC in children from 6 to 11 years of age with severe eosinophilic asthma, with an additional cohort of up to 3 Japanese patients aged 12 to 14 years.

Approximately 30 evaluable patients aged 6 to 11 years will be treated with benralizumab across the 2 combined weight strata, with a minimum of 8 patients in each stratum (Section 9.3). Up to 3 additional Japanese patients aged 12 to 14 years will be enrolled. Patients aged 6 to 11 years will be stratified by body weight at screening (<35 kg / ≥ 35 kg). Patients with a body weight <35 kg at screening will receive the following regimen of benralizumab: [REDACTED] mg administered by SC injection at Day 0 and Weeks 4, 8, and 16 (Part A), followed by [REDACTED] mg at Weeks 24, 32, and 40 (Part B). Patients with a body weight ≥ 35 kg at screening will receive the following regimen of benralizumab: [REDACTED] mg administered by SC injection at Day 0 and Weeks 4, 8, and 16 (Part A), followed by [REDACTED] mg at Weeks 24, 32, and 40 (Part B). Japanese patients aged 12 to 14 years will receive the [REDACTED] mg dose, and their visit schedules will be the same as patients aged 6 to 11 years throughout the study.

The study will be conducted in 2 parts, Part A and Part B. Part A will consist of 16 weeks of treatment to evaluate the PK and PD, and safety of benralizumab. Part B will consist of 32 weeks of continued treatment to evaluate the safety of benralizumab. All study data will be summarised together, not separately by study part.

After initial enrolment and confirmation of entry criteria, patients will proceed to a screening period of up to 28 days to allow adequate time for the eligibility criteria to be evaluated. The screening period may be extended if necessary after discussion with the AstraZeneca Study Physician. Patients who meet eligibility criteria will enter the 48-week treatment period. Patients will be maintained on their currently prescribed asthma maintenance therapy(ies) without change, from enrolment through screening, and through the treatment period.

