- 6 A well-documented requirement for regular treatment with ICS: total daily dose equivalent to ≥ 250 μg fluticasone propionate, or ≥ 400 μg budesonide (≥ 320 μg budesonide ex-actuator), or ≥ 200 μg fluticasone furoate, or ≥ 220 μg mometasone furoate, or ≥ 160 μg ciclesonide, or ≥ 1000 μg triamcinolone acetonide, or ≥ 500 μg beclomethasone dipropionate, or ≥ 200 μg beclomethasone dipropionate (HFA) in the 12 months prior to Visit 1, with or without maintenance oral corticosteroids. Medium dose ICS as per local guidelines will also satisfy the inclusion criterion after agreement with the Study Physician.
- 7 Current treatment with at least 1 additional controller medication, such as inhaled LABA, leukotriene receptor antagonist, long acting anti-muscarinic agent, or theophylline, since at least 3 months prior to Visit 1.
- 8 Forced expiratory volume in 1 second (FEV₁): Flow/ volume curve indicating airflow obstruction at either Visit 1 or 2 (performed prior to first dose of study medication), associated with: a pre-bronchodilator FEV₁ $\leq 110\%$ predicted normal, or, FEV₁/Forced Vital Capacity ratio ≤ 0.8 .

Weight

- 9 Body weight ≥ 15 kg.

Sex

- 10 Male or female

Reproduction

- 11 Females of childbearing potential (FOCBP) who are sexually active, as judged by the investigator, must commit to consistent and correct use of an acceptable method of contraception for the duration of the study and for 12 weeks after the last dose of IP.

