6.6 Concomitant therapy

Any medication or vaccine including over-the-counter or prescription medicines, vitamins, and/or herbal supplements that the patient is receiving at the time of enrolment or receives during the study must be recorded in the eCRF along with:

- Reason for use
- Dates of administration including start and end dates
- Dosage information including dose and frequency.

Restricted medications are listed in Table 4.

Table 4 Restricted medications

| Medication/class of drug: | Usage (including limits for duration permitted and special situations in which it's allowed): |
|--|---|
| Bronchodilator medication: SABA or SAMA Twice daily LABA or LAMA Once daily therapies containing LABA or LAMA | Should be withheld prior to scheduled spirometry for: 6 hours 12-24 hours ≥24 hours |
| Topical immunosuppressive medication | May be administered at the discretion of the investigator after discussion with the AstraZeneca Study Physician |
| Allergen immunotherapy injection | Should not be administered within 7 days of IP administration |
| Inactive/killed vaccines (eg, inactive influenza) | Should not be administered 7 days before or 7 days after IP administration |

Abbreviations: IP investigational product, LABA long-acting β 2 agonists, LAMA long-acting anti-muscarinic, SABA short-acting β 2 agonists, SAMA short-acting anti-muscarinic

Prohibited medications are listed in Table 5.

Table 5 Prohibited medications

| Prohibited medication/class of drug: | Duration |
|---|--|
| Immunosuppressive medication other than prior stable systemic corticosteroid for the maintenance treatment of asthma and for asthma exacerbations | Study period |
| Live attenuated vaccines | Within 30 days prior to first dose of IP, during the treatment period, and for 12 weeks (5 half-lives) after the last dose of IP |
| Oral or ophthalmic non-selective β -adrenergic antagonist (eg, propranolol) | Study period |
| Any marketed or investigational biologic (monoclonal or polyclonal antibody) | 4 months or 5 half-lives (whichever is longer) prior to Visit 1, during the treatment period, and 4 months or 5 half-lives (whichever is longer) after the last dose of the IP |
| Other IP | 30 days or 5 half-lives (whichever is longer) prior to first dose of IP and during the study period |

Abbreviations: IP investigational product

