7.1.1 Procedures for discontinuation of study treatment

A patient that decides to discontinue study treatment will always be asked about the reason(s) and the presence of any AEs. The date of last administration of study treatment should be documented in the eCRF. Patients permanently discontinuing study treatment should be given locally available standard of care therapy, at the discretion of the investigator.

All patients who prematurely discontinue IP should return to the study site and complete the procedures described for the Early Discontinuation (DXD) Visit within 4 weeks after the last dose of IP. At that visit, although no longer on IP, patients should be encouraged to remain in the study. Although only AEs, SAEs, and concomitant medication are required to be collected after the DXD Visit, safety data collection should continue according to the study protocol.

Note that in this case, the DXD Visit replaces the nearest regular visit while the following visits continue as possible. If the patient or guardian does not agree to continue in-person study visit(s), a modified follow-up, such as telephone contact with the patient or guardian, should be arranged to ensure the collection of safety information through the 48-week time point.

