8.4.6.1 Time period for detecting medical device deficiencies

- Medical device incidents or malfunctions of the medical device will be detected, documented, and reported during all periods of the study in which the medical device is used.
- If the investigator learns of any medical device deficiency at any time after a participant has been discharged from the study, and such incident is considered reasonably related to a medical device provided for the study, the investigator will promptly notify the sponsor.

The method of documenting Medical Device Deficiency is provided in [Appendix G](#).

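### The end of safety collection is stated inconsistently (Week 52 against Day 362, and Week 48 for some discontinuers), and reporting a related SAE after the last visit is optional as worded

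*Protocol*

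**What the plan says.** **End of collection.** Protocol 8.3.2 collects AEs and SAEs from signature of the consent form "throughout the treatment period and including the follow-up period (Visit 14"). Sections 1.2 and 4.1 place that follow-up visit at Week 52. Table 1 gives the study days of Visits 11 to 14 as "224 | 280 | 336 | 362", so the column headed Week 52 carries Day 362, with a window of ±7 days. SAP Table 1 repeats Week 52 with target day 362. It uses 308–348 as the Week 48 window for AEs and several other assessments, and ≥349 for follow-up.

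**Last dose.** Part B dosing is given as "mg at Weeks 24, 32, and 40 (Part B"), so the last scheduled dose is at Visit 12, Day 280 ±7. Section 6.3.4 requires a dose to be rescheduled for fever or intercurrent illness and gives no limit on the delay.

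**Discontinuers.** Section 7.1.1 asks that safety data go on being collected as the protocol provides. For a child who will not attend in person, however, remote contact "should be arranged to ensure the collection of safety information through the 48-week time point".

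**After the last visit.** For an SAE, including a death, that the investigator learns of and considers "reasonably related to the study treatment or study participation, the investigator may notify the sponsor". For a device deficiency learned of after discharge and considered reasonably related to the device, section 8.4.6.1 says "the investigator will promptly notify the sponsor".

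**Other post-dose periods.** Live vaccines are prohibited "for 12 weeks (5 half-lives) after the last dose of IP" (Table 5). Contraception is required "for the duration of the study and for 12 weeks after the last dose of IP" (inclusion criterion 11).

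**The concern.** Long-term safety is in the study title, and about 30 children are to be treated, so the AE window should have one definite end for every child. As written, three things vary. Two sites reading the same column of Table 1 could aim for follow-up visits two days apart. Two children who stop treatment early could have AEs collected to Week 52 or to Week 48, depending only on whether they still attend in person. A related serious event that comes to light after the last visit reaches the sponsor only if the investigator chooses to report it.

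The last of these matters most. The SAP's on-study AE period (3.1.3, 3.3.6.1) ends at study completion or withdrawal, so an event with later onset is outside the AE summaries in any case. Notification to the sponsor is then the only route by which it would be seen.

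**Working it through.** **1. Day label of Visit 14**

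Inputs: the Week and Day rows of Protocol Table 1. Rule tested: day = 7 × week.

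| Week | 1 | 2 | 4 | 8 | 12 | 16 | 24 | 32 | 40 | 48 | 52 |
|---|---|---|---|---|---|---|---|---|---|---|---|
| 7 × week | 7 | 14 | 28 | 56 | 84 | 112 | 168 | 224 | 280 | 336 | 364 |
| Stated day | 7 | 14 | 28 | 56 | 84 | 112 | 168 | 224 | 280 | 336 | 362 |

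Ten of eleven agree; only Week 52 fails. Day 362 appears in each part of Protocol Table 1 and again in the SAP, so it is not a reading error in one cell.

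**2. Follow-up after the last scheduled dose**

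Inputs: dose at Day 280 ±7; Visit 14 at Day 362 or 364, ±7.

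| | Visit 14 at Day 362 | Visit 14 at Day 364 |
|---|---|---|
| On schedule | 362 − 280 = 82 days | 364 − 280 = 84 days |
| Shortest in window | 355 − 287 = 68 days | 357 − 287 = 70 days |
| Longest in window | 369 − 273 = 96 days | 371 − 273 = 98 days |

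For reference only, 12 weeks is 12 × 7 = 84 days. The on-schedule difference of 2 days comes wholly from the Day label. The spread of 14 days either way comes from the two ±7-day windows and remains whichever label is right. A Week 40 dose rescheduled beyond its window would shorten the interval further.

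**3. SAP windows**

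SAP 3.1.4 puts the upper limit halfway between visits, less one day when the number of days between them is even.

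- Plan's own figure: (336 + 362)/2 = 349, less 1 = 348. This reproduces 308–348 and ≥349.
- With Day 364: (336 + 364)/2 = 350, less 1 = 349. This gives 308–349 and ≥350.

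Only an observation on Day 349 would change window. The follow-up window has no upper limit, so nothing recorded after Day 362 is lost.

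**4. Discontinuers followed remotely**

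- Loss against 8.3.2: 52 − 48 = 4 weeks of AE collection.
- A child who stops treatment prematurely will normally have had the last dose at Week 32 or earlier. On schedule, 336 − 224 = 112 days of follow-up remain.
- With a Week 32 dose 7 days late and the 48-week contact 7 days early, 329 − 231 = 98 days remain. Both exceed 84.

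**5. Notification after the study, side by side**

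| | Trigger | Duty |
|---|---|---|
| 8.3.2, SAE or death | learned of after the last visit and considered reasonably related | *may* notify |
| 8.4.6.1, device deficiency | learned of after discharge and considered reasonably related | *will promptly* notify |

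The triggers are parallel and the duties are not. The 24-hour rule in 8.4.1 is written for SAEs arising in the course of the study, so it does not clearly cover this case.

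**The case against.** A reader might infer that AE collection falls short of the protocol's own 12-week, 5 half-life risk period. The documents do not support that. The 12-week (5 half-life) period is set for live vaccines, and 12 weeks for contraception; no section applies either to AE collection. Table 5 also gives a different period for other biologics (4 months or 5 half-lives, whichever is longer), so the protocol has no single post-dose period. Week 40 to Week 52 is exactly 12 weeks, and intervals of 84 days or more are not short by any of these readings. Counting the shortfall in half-lives adds little: the documents state no numerical half-life, and the paediatric half-life is itself a primary endpoint. The 12-week comparison therefore stands only as a reference point.

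A reader might also infer that discontinuers as a group are followed for too short a time. The 48-week limit covers only those who decline in-person visits, and the 112-day and 98-day figures show that 12 weeks is normally still covered. An interval of 336 − 280 = 56 days would need a last dose at Week 40, and such a child has received every scheduled dose. What stands is that 7.1.1 and 8.3.2 disagree.

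On notification, 8.3.2 refers to Appendix C for SAE reporting procedures, and that appendix was not in the text available. It may contain a firm duty. If so, 8.3.2 contradicts it and still needs correcting; if not, the permissive wording governs. The device section answers to separate device regulations, so the comparison shows uneven wording and does not prove an error.

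Finally, the clinical consequence should not be overstated. Section 2.3 calls the helminth risk theoretical and reports no increase in AEs with anti-drug antibodies, and section 8.4.4 defines anaphylaxis as arising within minutes to hours.

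**Conclusion.** The point holds as two inconsistencies and one weak reporting duty.

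- **Week 52 against Day 362:** a 2-day discrepancy (82 or 84 days after an on-schedule last dose), carried from the protocol into the SAP. It breaks no stated minimum, because none is stated.
- **Section 7.1.1 against 8.3.2:** 4 weeks of AE collection lost for children who stop treatment and decline in-person visits. This is an inconsistent window, not a gap in the first 12 weeks after dosing, provided their last dose was at Week 32 or earlier.
- **Notification after the last visit:** optional, as 8.3.2 is worded, for a related SAE or death. This is the most consequential of the three and does not depend on any half-life or 12-week benchmark. It is subject to what Appendix C says.

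The arithmetic rests on the Day row and the ±7-day windows in Protocol Table 1. That follow-up is too short overall does not follow from the documents.

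**What to change.** 1. **Protocol Table 1 and SAP Table 1:** reconcile Week 52 with Day 362. If Week 52 is meant, use Day 364, set the SAP target day to 364, and change its windows to 308–349 and ≥350.
2. **Protocol 7.1.1:** run remote follow-up through Week 52 (Visit 14), to agree with 8.3.2.
3. **Protocol 8.3.2:** for SAEs, including deaths, considered related and learned of after the last visit, replace *may notify* with *will promptly notify*, and align the sentence with Appendix C.
4. **Optional:** when the Week 40 dose is delayed, time Visit 14 from the actual last dose, with a stated window including an upper limit. This is a design choice and does not correct an error. Changing to Day 364 alone still leaves 70–98 days.

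Cost: wording changes and one boundary in SAP Table 1. A few children have one extra telephone contact, and the last visit moves two days later if Day 364 is adopted. Visit 14 already exists and has no scheduled blood draw (Protocol Table 7).
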